### **3.4 Methods of Pooling Data**

For the purpose of adjusting for investigator effects in statistical models, investigator sites will be pooled into groups based on geographic region and number of subjects enrolled with an aim for comparable sample sizes among pooled investigator sites. Initial US geographic regions will consist of north east, east, south east, mid west, mid south, and west. These regions could be further sub-divided based on enrollment but no sites will be classified outside of their logical geographical region.

In terms of achieving comparable sample sizes, the goal of the pooling strategy will be to avoid less than a minimum number of subjects per pooled investigator site. The size of a pooled investigator site would generally not be larger than the total number of subjects enrolled at the highest enrolling individual investigator site. The pooled investigator sites will be used in all applicable analyses where adjustment for investigator effect is desired.

Based on an average of 6 subjects per site to be enrolled, the primary pooled investigator site strategy will target 10 pools of approximately 60 subjects each (approximately 30 per treatment group per pooled investigator site). As a sensitivity analysis, a second pooling will have a target of 20 pools of approximately 30 subjects each (approximately 15 per treatment group per pooled investigator site). The actual designation of membership in a pooled investigator site cannot be made until the final enrollment quantities and final number of sites used is completed. The final pooling strategy will be defined before treatment unblinding, and will be provided as an addendum to the SAP. The goals stated above will be adhered to as closely as possible.

### **3.5 Visit Windows**

Daily IVRS diary data are planned for daily collection starting on the day of the Screening visit and continuing until the planned Week 26 (Visit 9 Day 183).

Weekly IVRS diary data are planned for each week of the 2-week screening period (when applicable), and each week of the 26-week treatment period.

For all IVRS efficacy data, the date collected will be used to calculate a relative study day (Rel Day). The relative study day will be calculated as the number of days from the day of first dose. The day of the first dose date is Day 1. The preceding day is Day -1, the day before that is Day -2, etc. There is no Day 0.

Actual study periods will be defined as follows for the purposes of the efficacy evaluations:

- Screening/Baseline Period (Rel Days -14 through Day -1): For the average weekly CSBMs, average weekly SBMs, average weekly stool consistency, average weekly straining score, and average weekly abdominal symptom score (pain, discomfort, bloating, cramping, and fullness), the most recent 7 days will be used to calculate Week -1 values (i.e., days -1 through -7) and remaining days will be used for Week -2 calculations (i.e., day -8 through -14 or more if applicable). The baseline for these variables will then be based on the average of the week -2 and week -1 values. While the screening period may vary somewhat from 14 days, it will generally be required that subjects provide two weekly ratings of the weekly IVRS diary questions during this period.
- Treatment Period:
  - Week 1 (Rel Day 1-7)
  - Week 2 (Rel Day 8-14),
  - Week 3 (Rel Day 15-21),
  - Week 4 (Rel Day 22-28),
  - Week 5 (Rel Day 29-35),
  - Week 6 (Rel Day 36-42),
  - Week 7 (Rel Day 43-49),
  - Week 8 (Rel Day 50-56),
  - Week 9 (Rel Day 57-63),
  - Week 10 (Rel Day 64-70),
  - Week 11 (Rel Day 70-77),
  - Week 12 (Rel Day 78-84), and
  - Week 13 through Week 26 (Rel Day 85-183 divided by 7 day weeks).

The week during which the day of the last dose occurs will be considered the last valid week during the 26-week treatment period, assuming it contains at least 4 valid daily IVRS diary days. Otherwise, the last valid week will be the preceding week. The last valid week during the treatment period will be used as the endpoint week for weekly efficacy summaries. If the last valid week is before week 12, the week 12 endpoint and week 26 endpoint will use this week. If the last valid week is after week 12, the week 12 endpoint will use week 12 and week 26 endpoint will use the last valid week obtained after week 12.

Only data captured from the first dose until the last dose will be used to derive the weeks during the 26-week treatment period,

All data listings will contain a relative study day, regardless of whether the data was collected via IVRS diary or eCRF.

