4. INVESTIGATIONAL PLAN

This is a Phase 3, multi-center, randomized, double-blind, placebo controlled study of tenapanor in subjects with IBS-C. Patients who are 18 to 75 years old, meeting the definition of IBS-C as defined by the Rome III Criteria for the Diagnosis of IBS (see [Appendix A](#)) will undergo a battery of screening procedures to determine eligibility for the trial. A 2:1 screen to randomization ratio is expected.

The study will consist of a 2-week screening period, and a 26-week treatment period.

Two weeks prior to study randomization, prospective subjects may be assessed with respect to their meeting the eligibility requirements of the study.

At the beginning of the 2-week screening period (Day -14), subjects will be questioned with respect to their eligibility for the study. Those that meet the basic requirements will be asked to provide written informed consent. The basic screening assessments will include: evaluation of the inclusion/exclusion criteria, medical history (including details about co-morbid disorders), physical exam, vital signs, ECG, and clinical laboratory tests, including urinalysis. Subjects must discontinue the use of all prohibited medications at Visit 1 (Screening/Day -14) for the duration of the study, as referenced in [Section 5.6](#). During the screening period, and starting on the evening of Study Visit 1, subjects will self-report daily information about the status of their IBS symptoms via a touch-tone telephone diary. Each day, entries into the telephone diary (IVRS diary) must occur between 6PM and 11:59PM (local time). This will include information about their stool frequency, stool consistency, straining, abdominal pain, abdominal discomfort, abdominal bloating, abdominal fullness, abdominal cramping, and rescue medication usage. Additionally, on a weekly basis, the IBS severity and constipation severity will also be collected through the IVRS diary. Subject compliance with the electronic diary will be monitored actively by the site staff and by the electronic diary system.

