6.3. Treatments to be Administered

Study drug will be dispensed only to eligible subjects under the supervision of the Investigator or identified sub-Investigator(s). Eligible subjects will be randomized 1:1 into one of two treatment groups: tenapanor 50 mg BID or placebo BID. Subjects will take one tenapanor tablet or one matching placebo tablet twice daily, immediately prior to breakfast or the first meal of the day and immediately prior to dinner. On Day 1, the first dose should be taken immediately prior to dinner.

Subjects will receive one bottle of drug at Visit 2 (Day 1), Visit 4 (Day 29 ± 3), Visit 5 (Day 57 ± 3 days), Visit 6 (Day 85 ± 3 days), and Visit 7 (Day 113 ± 3 days) and **two** bottles of drug at Visit 8 (Day 141 ± 3 days). At each visit the subject will be asked to return their unused drug and bottles. Study drug compliance will be monitored closely by the clinical site staff and will be verified by the study monitor during on-site monitoring visits.

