8.3.2.1 Abdominal Pain

“How would you rate your worst abdominal pain over the past 24 hours? Please use the scale where 0 represents no abdominal pain and 10 represents very severe abdominal pain. Please enter a value between 0 and 10 followed by pound or hash sign.”

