8.3.2.6 Bowel Movement Frequency

“How many bowel movements have you had in the past 24 hours?”

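### Week 1 counts the Day 1 diary entry, most of which describes the hours before the first dose; the effect is small and conservative, and the SAP should leave that entry out

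*SAP*

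**What the plan says.** Five provisions have to be read together.

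- **Windows.** SAP 3.5 sets "Week 1 (Rel Day 1-7", and Protocol 10.6 is the same. SAP 3.5 also says "The day of the first dose date is Day 1", and that for diary data "the date collected will be used to calculate a relative study day (Rel Day". An entry is therefore placed by the date of the call, not by the hours it describes. Baseline stops at Day -1, so the Day 1 entry falls in Week 1.
- **First dose.** Protocol 6.3: "On Day 1, the first dose should be taken immediately prior to dinner". SAP 2.2.1 does not repeat this instruction.
- **Call times.** Protocol 4: "entries into the telephone diary (IVRS diary) must occur between 6PM and 11:59PM (local time". SAP 2.2 gives the same window.
- **Recall.** Protocol 8.3.2.6 asks "How many bowel movements have you had in the past 24 hours" and Protocol 8.3.2.1 asks "How would you rate your worst abdominal pain over the past 24 hours". The clock time of each bowel movement is collected. Pain is a single score for the whole period.
- **Limiting rule.** SAP 3.5, with the same sentence in Protocol 10.6: "Only data captured from the first dose until the last dose will be used to derive the weeks during the 26-week treatment period".

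Week 1 is one of the 12 weeks in the primary 6/12 rule. It also enters the 9/12 and 13/26 rates, the weekly responder rates and the weekly change-from-baseline analyses.

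**The concern.** An evening call on the day of a pre-dinner first dose reports mainly on untreated hours, yet it supplies one of the seven days of a treatment week. The worst-pain item makes this harder to repair: a 24-hour maximum cannot fall below the worst pain felt before dosing, and one score cannot be split at the time of the dose.

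The limiting rule does not settle the matter. A call made after dinner satisfies it on its wording, although most of what it recalls is pre-dose. A call at 18:00 before a 19:00 dinner fails it, yet the date rule still assigns that entry to Week 1. No comparison of dose time with call time is specified, so two programmers could derive Week 1 differently.

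At stake are the Week 1 results themselves, which understate early effect, and to a much smaller degree the responder counts to which Week 1 contributes.

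**Working it through.** **1. The plan's power figure.** Inputs from SAP 3.1: 300 per arm, 45% vs 30%, two-sided Fisher's exact test at 0.05. Exact enumeration gives 96.1% (stated 95%). For an 11.6-point difference, 45% vs 33.4% gives 80.8% and 56.6% vs 45% gives 80.2% (stated 80%). Both statements reproduce and are not in dispute. They are the yardstick for step 5.

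**2. Pre-dose share of the Day 1 recall.** Share = 1 − max(0, call time − dose time)/24. Dinner time is assumed to lie between 17:00 and 20:00.

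| Dinner | Call 18:00 | Call 21:00 | Call 23:59 |
|---|---|---|---|
| 17:00 | 95.8% | 83.3% | 70.9% |
| 18:00 | 100% | 87.5% | 75.1% |
| 19:00 | 100% | 91.7% | 79.2% |
| 20:00 | 100% | 95.8% | 83.4% |

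**3. Effective Week 1 thresholds.** Suppose Day 1 sits at baseline level and v days are reported, Day 1 among them.

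- Pain: with baseline B and reduction r on the other v − 1 days, the weekly mean is B × [1 − r(v − 1)/v]. Meeting the 30% criterion needs r ≥ 0.30 × v/(v − 1).
- CSBMs: with a gain g per week on the other days, the standardised weekly change is g(v − 1)/v. Meeting the criterion of 1 needs g ≥ v/(v − 1).

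| Days reported | Pain reduction needed | CSBM gain needed |
|---|---|---|
| 7 | 0.30 × 7/6 = 35% | 7/6 = 1.17 |
| 4 (the minimum) | 0.30 × 4/3 = 40% | 4/3 = 1.33 |

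**4. Week 1 responder rates (illustrative simulation, all inputs assumed).** Daily CSBMs are Poisson with a mean baseline of 0.35 per week. Mean gain is 1.5 or 2.5 per week on active and 0.7-1.2 on placebo. Pain reduction is beta(1.2, 2.2) on active and beta(1.2, 2.8) or beta(1.2, 3.5) on placebo. Daily pain noise has SD 1.2, and the baseline pain level is also assumed. The comparison is the plan's Days 1-7 against seven fully on-drug days.

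- Active arm: 25.7% vs 31.4% and 30.7% vs 37.0%, losses of 5.7 and 6.3 points.
- Placebo arm: losses of 4-5 points.
- Between-arm difference: a loss of 0.9-1.9 points.

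Six scaled days (Days 2-7) recover about 3-5 points in the active arm. They recover from 0.6 to about 2 points of the between-arm difference, depending on the assumptions.

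**5. Primary endpoint.** Week 1 decides the outcome only for subjects with exactly 5 response weeks among Weeks 2-12. With weekly response probability p varying between subjects as a beta distribution, and Week 1 response multiplied by f in both arms:

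P(responder) = E[ P(Bin(11, p) ≥ 6) + P(Bin(11, p) = 5) × f × p ]

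This is calibrated to 45% vs 30% at f = 1, with intra-subject correlation of 0.2-0.6 (assumed).

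| Week 1 response | 6/12 difference | Fisher power |
|---|---|---|
| Unaffected (f = 1) | 15.0 points | 96.1% |
| Cut by 30% (f = 0.7) | 14.7-14.9 points | 95.8-96.0% |
| Nobody responds in Week 1 (f = 0) | 14.1-14.7 points | 95.1-95.8% |

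The active-arm cuts in step 4 are milder than f = 0.7: 5.7/31.4 = 18% and 6.3/37.0 = 17%. A 15% cut (f = 0.85) lowers the difference to 14.86-14.95 points, a loss of 0.05-0.14. About 0.1-0.2 points is therefore a fair summary. The 9/12 and 13/26 rates were not modelled separately.

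**The case against.** The strongest reply is that this hardly matters. Counting from the date of first dose is a coherent convention. The handling is identical in both arms, and the primary result barely moves. The Week 1 summaries are secondary variables whose p-values both documents call descriptive, and neither document lists speed of onset as an objective or an efficacy variable. The limiting rule can be read as already removing a call made before the dose, and recorded bowel-movement times would let pre-dose movements be identified. Protocol 10 also says that the primary and key secondary analyses will stay the same in the SAP.

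Most of this stands, and it fixes the size of the point. It does not remove the point. No clock-time rule is written, the pain score cannot be divided, and the stated windows put mostly pre-dose information into a treatment week.

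Three stronger readings are tempting, and the documents do not support them.

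- *The Week 1 treatment effect loses 5-6 points.* That is the active arm alone, measured against seven on-drug days. Placebo subjects have the same Day 1, so most of the loss cancels.
- *The primary analysis is compromised.* Under the null the arms are treated alike, so type I error is unaffected. Even the extreme case in the working keeps power above the stated 95%.
- *The Day 1 entry is wholly untreated.* Up to about 7 of its 24 hours can follow the dose. If the day's worst pain would have come in those hours, the score could still be lowered by treatment.

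**Conclusion.** The point holds as a small, conservative misclassification together with an unclear rule. The Day 1 entry is roughly 70-100% pre-dose if dinner falls between 17:00 and 20:00. If that day is at baseline level, it raises the effective Week 1 thresholds to 35% and 1.17 CSBMs per week in both arms when all seven days are reported. The threshold arithmetic is exact under that assumption. The losses of about 1-2 points in the Week 1 difference and about 0.1-0.2 points in the 6/12 difference rest on assumed distributions and should be read as orders of magnitude. The change is worth making because it costs almost nothing, not because the trial's conclusion depends on it.

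**What to change.** Before unblinding, amend SAP 3.5 as follows.

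1. Define Week 1 as Rel Days 2-7 for all daily diary variables. Keep the 7-day standardisation and the 4-day valid-week rule, which both work with six days.
2. Assign the Day 1 entry to neither baseline nor a treatment week. Moving it into Week -1 would be wrong: it could bring post-randomisation, post-dose hours into baseline.
3. State that *captured*, in the first-dose-to-last-dose sentence, refers to the period recalled, and apply it at the start of treatment by study day rather than clock time: Day 1 out, Day 2 onward in. A strict clock rule would needlessly drop some Day 2 entries. With a 20:00 dinner and an 18:00 call the next day, only 2/24 = 8% of the Day 2 recall is pre-dose.
4. Record the departure from Protocol 10.6 in the SAP. Protocol 10 allows changes to that section to be handled there without a protocol amendment.

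If the sponsor prefers to keep the protocol window for the primary and key secondary endpoints, apply Days 2-7 to the Week 1 weekly summaries and prespecify the primary analysis without Day 1 as a sensitivity analysis.

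The cost is a short edit to the SAP and the programming specification, in a list that needs correcting anyway because Rel Day 70 appears in both Week 10 and Week 11. The statistical price is that a valid Week 1 then needs four of six possible days instead of four of seven, and that six-day averages are slightly noisier.

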10.6. Visit Windows

Daily IVRS diary data are planned for daily collection starting on the day of the Screening visit and continuing until the planned Week 26 (Visit 9 Day 183) visit.

Weekly IVRS diary data are planned for each week of the 2-week screening period (when applicable) and each week of the 26-week treatment period.

For all IVRS efficacy data, the date collected will be used to calculate a relative study day (Rel Day). The relative study day will be calculated as the number of days from the day of first dose. The day of the first dose date is Day 1. The preceding day is Day -1, the day before that is Day -2, etc. There is no Day 0.

Actual study periods will be defined as follows for the purposes of the efficacy evaluations:

- Screening/Baseline Period (Rel Days -14 through Day -1): For the average weekly CSBMs, average weekly SBMs, average weekly stool consistency, average weekly straining score, and average weekly abdominal symptom score (pain, discomfort, bloating, cramping, and fullness), the most recent 7 days will be used to calculate Week -1 values (i.e., days -1 through -7) and remaining days will be used for Week -2 calculations (i.e., day -8 through -14 or more if applicable). The baseline for these variables will then be based on the average of the week -2 and week -1 values. While the screening period may vary somewhat from 14 days, it will generally be required that subjects provide two weekly ratings of the weekly IVRS diary questions during this period.
- Treatment Period:
 - Week 1 (Rel Day 1-7)
 - Week 2 (Rel Day 8-14),
 - Week 3 (Rel Day 15-21),
 - Week 4 (Rel Day 22-28),

- Week 5 (Rel Day 29-35),
- Week 6 (Rel Day 36-42),
- Week 7 (Rel Day 43-49),
- Week 8 (Rel Day 50-56),
- Week 9 (Rel Day 57-63),
- Week 10 (Rel Day 64-70),
- Week 11 (Rel Day 71-77),
- Week 12 (Rel Day 78-84),
- Week 13 (Rel Day 85-91),
- Week 14 (Rel Day 92-98),
- Week 15 (Rel Day 99-105),
- Week 16 (Rel Day 106-112),
- Week 17 (Rel Day 113-119),
- Week 18 (Rel Day 120-126),
- Week 19 (Rel Day 127-133),
- Week 20 (Rel Day 134-140),
- Week 21 (Rel Day 141-147),
- Week 22 (Rel Day 148-154),
- Week 23 (Rel Day 155-161),
- Week 24 (Rel Day 162-168),
- Week 25 (Rel Day 169-175), and
- Week 26 (Rel Day 176-182).

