A key secondary efficacy variable will be the overall CSBM responder rate. An overall CSBM responder will be defined as a weekly CSBM responder for the first 6/12 weeks where the CSBM response criteria were met for the week. The weekly CSBM responder rates will be summarized for each week of the treatment period. An endpoint week will be defined as the last valid week during the treatment period with a CSBM response criteria assessment.

The average weekly CSBMs will be calculated as the sum of the number of CSBMs reported during each day of the defined weekly period divided by the number of days CSBMs were reported multiplied by 7. A valid week will require at least 4 days of SBM reporting. The average weekly CSBMs and change from baseline (where baseline is the average of the 2-weeks during the screening period) for each week of the treatment period will be summarized. An endpoint week will be defined as the last valid week during the treatment period with an average weekly CSBM.

The abdominal pain response criterion is defined as a decrease of 30% or more of percent change in average weekly worst abdominal pain from baseline. Abdominal pain will be scored daily using the scale 0 = No pain to 10 = very severe pain. The average weekly abdominal pain score will be calculated as the average score for all days during a valid week. A valid week will require at least 4 days of abdominal pain reporting. Should a subject not have data reported for a given week (either due to a gap in reporting or due to discontinuation), the subject will be considered to be a non-responder for the week.

The average weekly abdominal pain score and percent change from baseline (where baseline is the average of the 2-weeks during the screening period) for each week of the treatment period will be summarized. An endpoint week will be defined as the last valid week during the treatment period with an average weekly abdominal pain score.

A key secondary efficacy variable will be the overall abdominal pain responder rate. An overall abdominal pain responder will be defined as a weekly abdominal pain responder for the first 6/12 weeks where the abdominal pain response criteria were met for the week.

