Additional key secondary efficacy variables consist of the overall responder rate, overall CSBM responder rate, and overall abdominal pain responder rate calculated using a 13/26 week response criteria. These responder rates encompass the entire 26-week treatment period. Hence, for 13 out of the 26 weeks during the treatment period, the subject met the responder criteria for the 6/12 week responder rates.

Additional key secondary efficacy variables consist of the overall responder rate, overall CSBM responder rate, and overall abdominal pain responder rate calculated using a 9/12 week response criteria. Hence, for 9 out of the first 12 weeks during the treatment period, the subject met the responder criteria for the 6/12 week responder rates. In addition, for the first 9/12 week CSBM responder criteria, it is also required that the average weekly CSBMs for the week are  $\geq 3$ .

For each of the efficacy variables described above (i.e., first 6/12, 13/26, and first 9/12 responders for respective weeks), several sensitivity analyses will be done. Instead of assuming non-response for missing weeks or weeks with less than 4 days of valid diary data, a sensitivity analysis will be carried out imputing response for these weeks. Similarly, instead of assuming a 30% reduction for percent change in abdominal pain, these analyses will be repeated using a 40% reduction and a 50% reduction as response criteria. Note that for these last 2 analyses, the CSBM responder analyses will not be repeated, only the overall and abdominal pain responder rates.

Secondary efficacy variables will include the following:

The durable overall responder rate, durable overall CSBM responder rate, and durable overall abdominal pain responder rate will be secondary efficacy variables. The durable responder rates use the same first 9/12 week response criteria and in addition, require the last 3/4 weeks of the first 12 weeks of the treatment period to meet the response criteria.

The proportion of subjects with  $\geq 3$  CSBMs per week will be summarized for the baseline and treatment periods. An endpoint week will be defined as the last valid week during the treatment period with an average weekly CSBM.

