### **3.3 Procedures for Handling Missing Data**

The primary analysis will be based on the observed data where average weekly SBMs and CSBMs will be standardized to 7-day frequencies. This amounts to missing days during the week being imputed with the mean for the non-missing days. A valid week will require at least 4 non-missing diary days. Hence, for the primary analysis, weeks with less than 4 diary days are treated as a non-responder for that week. To further assess the impact of missing weeks on the efficacy analyses, a sensitivity analysis will be carried out by treating weeks with less than 4 diary days as a responder for that week.

The valid week rule will also apply for stool consistency and straining score although it is assumed that if the diary was filled out for frequency of stools, it would also be filled out with respect to these items. However, the average weekly stool consistency and the average weekly straining score will be calculated on the observed number of responses without any standardization. For the purposes of calculating an average, days with no stools reported (i.e., a 0 was recorded for the answer to IVRS question) will be scored as 0 for average weekly stool consistency and average weekly straining score.

An endpoint week will be defined as the last valid week during the first 12-weeks of the treatment period and the last valid week of the 26-week treatment period where each weekly

efficacy variable was obtained. This amounts to creating an endpoint last observation carried forward such that each subject's endpoint value represents the last experience while receiving study drug during the first 12-weeks and the total 26-week treatment period. In the few cases where no efficacy data is collected during the 12-week treatment period, the endpoint week will be considered a non-response or missing if no frequency or stool consistency data are obtained.

Otherwise, all other observed data will be used in the analyses.

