### **3.7.1 Efficacy Analyses**

The primary objective of this study will be to demonstrate the superiority of tenapanor over placebo in the proportion of subjects who are weekly overall responders at 6 or more of the first 12 weeks of treatment.

The ITT analysis set will be used for the analysis of the primary, key secondary, secondary, and all sensitivity analyses. The PP analysis set will be used for the analysis of the primary, key secondary, and secondary variables as a separate sensitivity analysis. All efficacy analyses will be carried out based on observed cases (OC) with imputation as described previously in [Section 3.3](#).

All efficacy variables involving responder rates or proportions will be analyzed using a Cochran-Mantel-Haenszel (CMH) test with pooled investigator site as a stratification (adjustment) variable. These analyses include subject based variables and variables summarized weekly. Summary statistics will include the pairwise risk difference with placebo along with the asymptotic 95% confidence interval (CI). The adjusted relative risk (adjusted for pooled investigator site) will be based on the ratio of responder rates for tenapanor 50 mg BID versus placebo. The 95% CI versus placebo will also be presented for the adjusted relative risk.

All change from baseline or percent change from baseline continuous efficacy variables derived from the daily IVRS questions (i.e., average weekly CSBMs, SBMs, stool consistency, straining score, abdominal symptoms of pain, discomfort, bloating, fullness, and cramping), as well as the weekly IBS severity, constipation severity, and IBS QOL will be analyzed using an analysis of covariance (ANCOVA) model with terms for pooled investigator site, treatment, and baseline as the covariate. These analyses include variables summarized weekly or on a visit basis.

Actual values for degree of relief of IBS symptoms and treatment satisfaction will be analyzed using an analysis of variance (ANOVA) model with terms for pooled investigator site and treatment.

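### SAP 3.5 puts Day 70 in both Week 10 and Week 11, giving an 8-day Week 11 that contradicts the protocol and feeds the primary 6/12 endpoint

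*SAP*

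**What the plan says.** SAP 3.5 defines the study periods used for the efficacy evaluations. Two consecutive entries read "Week 10 (Rel Day 64-70") and "Week 11 (Rel Day 70-77"). Protocol 10.6 has the same Week 10 but gives "Week 11 (Rel Day 71-77").

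The window determines which diary days enter three weekly derivations:

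- **CSBM count (SAP 2.3.1).** The sum over the week is "divided by the number of days CSBMs were reported multiplied by 7".
- **Pain (SAP 2.3.1).** "The average weekly abdominal pain score will be calculated as the average score for all days during a valid week".
- **Validity (SAP 3.3).** "A valid week will require at least 4 non-missing diary days"; a week that falls short is a non-response in the primary analysis.

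The primary comparison in SAP 3.7.1 is the proportion of subjects who are "weekly overall responders at 6 or more of the first 12 weeks of treatment". The durable rates (SAP 2.3.1) also "require the last 3/4 weeks of the first 12 weeks of the treatment period to meet the response criteria", and Week 11 is one of those four weeks.

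Protocol 10 says that changes to its statistical section will be dealt with in the SAP, but that the primary and key secondary analyses will stay as they are. SAP 1 rules out any deviation from the primary analyses.

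**The concern.** The weekly windows should cover Days 1 to 84 once each in 7-day blocks. The SAP's do not, because Day 70 is used twice. This is an operative derivation rule. Since the protocol hands changes in its statistical section to the SAP, a programmer could reasonably treat 70 to 77 as superseding 71 to 77. A programmer who silently used 71 to 77 would instead depart from the SAP as written.

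At stake is the Week 11 value of every diary variable for any subject with a Day 70 entry. For borderline subjects, the Week 11 responder status that feeds the primary, key secondary and durable rates is also at stake.

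**Working it through.** **Window lengths.** Contiguous 7-day weeks from Day 1 run from 7(k − 1) + 1 to 7k. For k = 11 this gives 71 to 77, the protocol's entry. The formula reproduces all 26 protocol windows and every other SAP window in Weeks 1 to 12.

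- SAP Week 10: 70 − 64 + 1 = 7 days.
- SAP Week 11: 77 − 70 + 1 = 8 days.
- SAP Weeks 1 to 12: 11 × 7 + 8 = 85 day-slots for 84 days. Day 70 is the only duplicate and there is no gap.

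**CSBM criterion (increase of at least 1 from baseline), complete diary.** Let k be the CSBMs in Days 71 to 77, d those on Day 70, and b the baseline. The protocol requires k − b ≥ 1. The SAP requires (k + d) × 7/8 − b ≥ 1. Illustrative cases:

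| b | k | d | Protocol weekly value | SAP weekly value | Change under the SAP |
|---|---|---|---|---|---|
| 0 | 1 | 0 | 1 (meets) | 0.875 (fails) | lost |
| 1 | 2 | 0 | 2 (meets) | 1.75 (fails) | lost |
| 2 | 3 | 0 | 3 (meets) | 2.625 (fails) | lost |
| 0.5 | 1 | 1 | 1 (fails) | 1.75 (meets) | gained |
| 1.5 | 2 | 1 | 2 (fails) | 2.625 (meets) | gained |
| 2.5 | 3 | 1 | 3 (fails) | 3.5 (meets) | gained |
| 0 | 0 | 2 | 0 (fails) | 1.75 (meets) | gained |
| 1 | 1 | 2 | 1 (fails) | 2.625 (meets) | gained |
| 2 | 2 | 2 | 2 (fails) | 3.5 (meets) | gained |

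No response is lost at baselines 0.5, 1.5 or 2.5. Rescaling to 7 days removes the inflation from an eighth day but not the influence of Day 70.

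The 9/12 and durable CSBM criteria also require at least 3 CSBMs in the week. Three CSBMs in Days 71 to 77 and none on Day 70 give 3.0 under the protocol and 3 × 7/8 = 2.625 under the SAP.

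**Pain criterion (at least 30% decrease), with an assumed baseline of 6.**

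- Pain 4 on each of Days 71 to 77 and 6 on Day 70. Protocol: 28/7 = 4.00, a decrease of 33.3% (meets). SAP: (28 + 6)/8 = 4.25, a decrease of 29.2% (fails).
- Days 71 to 77 summing to 30 and Day 70 = 3. Protocol: 30/7 = 4.286, a decrease of 28.6% (fails). SAP: (30 + 3)/8 = 4.125, a decrease of 31.3% (meets).

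**Validity.** Day 70 plus only three of Days 71 to 77 makes 4 diary days under the SAP (valid) and 3 under the protocol (invalid, hence a non-response). Because SAP 3.5 uses data only up to the last dose, a subject with a full diary and a last dose on Day 73 is such a case. That subject's endpoint week would also move from Week 10 to Week 11.

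**When Week 11 is decisive.**

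- 6/12: exactly 5 responses in the other 11 weeks.
- 9/12: exactly 8 in the other 11.
- 13/26: exactly 12 in the other 25.
- Durable: at least 8 in the other 11 and at least 2 among Weeks 9, 10 and 12, with one of these counts exactly at its minimum.

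**Size of the decisive group for 6/12.** The documents give planning rates of 45% and 45 − 15 = 30% (SAP 3.1) but no within-subject correlation of weekly response. Assume a beta-binomial model calibrated so that the probability of at least 6 of 12 equals those rates. For an assumed correlation of 0.2 to 0.6, between 4% and 12% of subjects have exactly 5 responses in the other 11 weeks. At zero correlation the range is 21% to 24%. This is a ceiling, because only those whose Week 11 status also flips are affected.

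**Weeks 13 to 26 (side point).** The SAP gives Days 85 to 183: 183 − 85 + 1 = 99 days, whereas 14 × 7 = 98. The protocol ends Week 26 at Day 182.

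**The case against.** The strongest reply is that this is an obvious one-digit misprint. Every other listed window is 7 days and contiguous, the protocol prints 71 to 77, counts are standardised to 7 days, and both documents say the primary analysis will not change. The worked cases are chosen at the threshold. A weekly overall response needs the CSBM and pain criteria in the same week, so a flip in one matters only if the other is met. The rule is the same in both blinded arms, so no direction of bias is shown. Whether the overlap was coded depends on a programming specification that SAP 4 places in a separate document.

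All of this stands as a limit on size. It does not make the text right: the SAP is the document that governs derivation, and it contradicts the protocol on a rule for the primary endpoint.

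On Weeks 13 to 26 the reply is largely correct. The SAP says the range is split into 7-day weeks, which weighs against an 8-day Week 26. If Day 183 stands alone, the preceding-week fallback in SAP 3.5 already makes Week 26 the endpoint week.

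**Conclusion.** The SAP's Week 11 window is wrong as written: it has 8 days, Day 70 is counted twice, and it conflicts with Protocol 10.6. Taken literally, it can change Week 11 values, validity and responder status, in both directions.

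The expected effect on the primary result is small. It is confined to subjects with exactly 5 responses in the other 11 weeks whose Week 11 status also flips, and the same rule applies to both arms. The documents do not give the stool, pain or correlation figures needed to put a number on the net shift. The 4% to 12% ceiling rests on the assumed model and correlation, and the pain cases on an assumed baseline of 6.

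The Weeks 13 to 26 range is a minor inconsistency that cannot touch the primary endpoint.

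**What to change.** Before unblinding:

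1. Change SAP 3.5 so that Week 11 is Days 71 to 77.
2. Confirm that the programming specification uses 71 to 77.
3. List Weeks 13 to 26 as in Protocol 10.6 (85 to 91 through 176 to 182), with one sentence saying that Week 26 is a 7-day week and Day 183 does not extend it.

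The cost is one digit, the list of later windows with its sentence, and a check of one table. It needs no new data and restores the window the protocol already specifies for the primary analysis.
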